## Appendix F. ECOG Performance Status and NYHA Classification

### Eastern Cooperative Oncology Group (ECOG) Performance Status

0. - Fully active, able to carry on all pre-disease performance without restriction
1. - Restricted in physically strenuous activity, but ambulatory and able to carry out work of a light or sedentary nature (eg, light housework, office work)
2. - Ambulatory and capable of all selfcare, but unable to carry out any work activities. Up and about more than 50% of waking hours
3. - Capable of only limited selfcare, confined to bed or chair more than 50% of waking hours
4. - Completely disabled. Cannot carry out any selfcare. Totally confined to bed or chair
5. - Dead

### New York Heart Association Functional Classification

1. Class I No limitation of physical activity. Ordinary physical activity does not cause undue fatigue, palpitation or dyspnea.
2. Class II Slight limitation of physical activity. Comfortable at rest, but ordinary physical activity results in fatigue, palpitation or dyspnea.
3. Class III Marked limitation of physical activity. Comfortable at rest, but less than ordinary activity causes fatigue, palpitation or dyspnea.
4. Class IV Unable to carry out any physical activity without discomfort. Symptoms of cardiac insufficiency may be present even at rest. If any physical activity is undertaken, discomfort is increased.

Approved

## Appendix G. Definition of Relapsed or Refractory Progressive Disease and Line of Therapies

**Relapsed disease** is defined as progression occurs in the absence of therapy.

**Refractory disease** is defined as disease that is nonresponsive while on primary or salvage therapy, or progresses within 60 days of last therapy.

**Progressive Disease for patients with Multiple Myeloma** requires any one or more of the following:

- Increase of  $\geq 25\%$  from lowest response value in any of the following
  - Serum M-component and/or (the absolute increase must be  $\geq 0.5$  g/dl)
  - Urine M-component and/or (the absolute increase must be  $\geq 200$  mg/24 h)
  - Only in patients without measurable serum and urine M-protein levels: the difference between involved and uninvolved FLC levels (the absolute increase must be  $> 10$  mg/dl)
  - Bone marrow plasma cell percentage: the absolute % must be  $> 10\%$
- Definite development of new bone lesions or soft tissue plasmacytomas or definite increase in the size of existing bone lesions or soft tissue plasmacytomas
- Development of hypercalcemia (corrected serum calcium  $> 11.5$  mg/dl or  $2.65$  mmol/l) that can be attributed solely to the plasma cell proliferative disorder

**A line of therapy** is defined as one or more cycles of a planned treatment program. This may consist of one or more planned cycles of single-agent therapy or combination therapy, as well as a sequence of treatments administered in a planned manner. For example, a planned treatment approach of induction therapy followed by autologous stem cell transplantation, followed by maintenance is considered one line of therapy. A new line of therapy starts when a planned course of therapy is modified to include other treatment agents (alone or in combination) as a result of disease progression, relapse, or toxicity. A new line of therapy also starts when a planned period of observation off therapy is interrupted by a need for additional treatment for the disease (Rajkumar, 2011).

**Progressive disease in patients with AML** is defined as:

Evidence for an increase in bone marrow blast percentage and/or increase of absolute blast counts in the blood:

- > 50% increase in marrow blasts over baseline (a minimum 15% point increase is required in cases with < 30% blasts at baseline; or persistent marrow blast percentage of > 70% over at least 3 mo; without at least a 100% improvement in ANC to an absolute level ( $> 0.5 \times 10^9/L$  [500/uL], and/or platelet count to  $> 50 \times 10^9/L$  [50,000/uL] nontransfused); or
- >50% increase in peripheral blasts (WBC x % blasts) to  $>25 \times 10^9/L$  ( $>25,000/uL$ ) (in the absence of differentiation syndrome)†; or
- New extramedullary disease

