## **Rules for Permanent Discontinuation**

Subjects will permanently discontinue from the investigational product if:

- Subjects experience adverse events meeting the DLT criteria at any time. Subjects will be followed until the DLT is resolved, returns to baseline value or is considered stable. Subjects will be withdrawn from AMG 397 treatment and will be treated as deemed appropriate by the investigator or treating physician. Except for:
  - Subjects showing evidence of response or subjects who in the opinion of the investigator may be responding to AMG 397, may have the option to continue therapy once the adverse events recover to baseline or Grade 1 and the re-introduction of AMG 397 is deemed safe by the investigator, Amgen's medical monitor, and Global Safety Officer. The subject should restart at a reduced dose.
  - Subjects who experience TLS as detail, see [Section 6.2.1.1.1](#) for dosing details.
- Intolerability of the study treatment
- The dosing is delayed > 4 weeks due to AMG 397-related adverse events
- Disease progression according to IMWG (MM), Lugano classification (NHL), or 2017 ELN response criteria (AML) and/or per institutional guidelines as applicable
- Clinical significant deterioration of health status
- Withdrawal of informed consent
- Subject becomes pregnant or is breastfeeding
- Initiation of new systemic anti-cancer therapy not provided in this study
- Study is terminated by the sponsor.

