Calcium $\leq$ 7.0 mg/dL (1.75 mmol/L) AND Patient symptomatic (e.g., muscle cramps, hypotension, tetany, cardiac arrhythmias)	
 
Administer calcium gluconate 50 to 100 mg/kg IV slowly with ECG monitoring.
 
Telemetry.
 
Recheck potassium, phosphorus, uric acid, calcium and creatinine in 1 hour STAT.
 
If calcium normalized 1 hour later, repeat potassium, phosphorus, uric acid, calcium and creatinine 2 and 4 hours later, if no other evidence of tumor lysis.
 
Calculate corrected calcium and check ionized calcium if albumin low.
 

Hyperphosphatemia	
Phosphorus $\geq$ 5.0 mg/dL (1.615 mmol/L) with $\geq$ 0.5 mg/dL (0.16 mmol/L) increase	
 
Administer a phosphate binder (e.g., aluminum hydroxide, calcium carbonate, sevelamer hydroxide, or lanthanum carbonate).
 
Nephrology (or other acute dialysis service) notification (dialysis required for phosphorus <math>\geq</math> 10 mg/dL).
 
Recheck potassium, phosphorus, uric acid, calcium and creatinine in 1 hour STAT.
 
If phosphorus <math><</math> 5.0 mg/dL 1 hour later, repeat potassium, phosphorus, uric acid, calcium and creatinine 2 and 4 hours later, if no other evidence of tumor lysis.
 

Creatinine	
Increase $\geq$ 25% from baseline	
 
Start or increase rate of IV fluids.
 
Recheck potassium, phosphorus, uric acid, calcium and creatinine in 1 to 2 hours STAT.
 

Approved

## 6.6 Support Care Guidelines for AMG 397

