MR	
 
• 25%–49% reduction in the level of serum M-protein and a 50%–89% reduction in 24 hour urinary M-protein, which still exceeds 200 mg per 24 hours
 
• If the serum and urine M-protein are not measurable, a decrease of 25%–49% in the difference between involved and uninvolved FLC levels is required in place of the M-protein criteria.
 
• If present at Baseline, a 25%–49% reduction in the size of soft tissue plasmacytomas is also required
 

Stable disease	
 
• Not meeting criteria for CR, VGPR, PR, or PD
 

Approved

Footnotes defined on next page

Response Subcategory a	Multiple Myeloma Response Criteria
PD b	
Any one or more of the following:
 

• Increase of <math>\geq 25\%</math> from lowest response value in:

➢ Serum M-component and/or (the absolute increase must be <math>\geq 0.5</math> g/dL)

○ Urine M-component and/or (the absolute increase must be <math>\geq 200</math> mg/24 h)

○ Only in patients without measurable serum and urine M-protein levels; the difference between involved and uninvolved FLC levels. The absolute increase must be <math>>10</math> mg/dL

➢ Bone marrow plasma cell percentages (absolute percentage must be <math>\geq 10\%</math>)

• Definite development of new bone lesions or soft tissue plasmacytomas or definite increase in the size of existing bone lesions or soft tissue plasmacytomase, f, g

• Development of hypercalcemia (corrected serum calcium <math>> 11.5</math> mg/dL or <math>2.65</math> mmol/L) that can be attributed solely to the plasma cell proliferative disorder

Page 2 of 2

Source: Durie 2006; Rajkumar 2011 (modified for protocol purposes).

CR = complete response; sCR = stringent complete response; FLC = serum light chain; MR = minor response; PD = progressive disease; PR = partial response; SFLC = serum free light chain; VGPR = very good partial response

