**Note:** Patients with measurable disease in both serum (SPEP) and urine (UPEP) at study entry are required to meet response criteria in both UPEP and SPEP in order to qualify for a MR or better. Conversely, it should be noted criteria for PD only needs to be met, and confirmed, in 1 parameter. For patients without measurable protein on UPEP at Baseline, UPEP will need to be repeated to confirm a response.

- a Patients with measurable disease in both serum (SPEP) and urine (UPEP) at study entry are required to meet response criteria in both UPEP and SPEP in order to qualify for a MR or better. Conversely, it should be noted that criteria for PD only needs to be met, and confirmed, in one parameter.
- b **All response categories (CR, sCR, VGPR, PR) require 2 consecutive assessments** made at any time before the institution of any new therapy, as well as no known evidence of progressive or new bone lesions if radiographic studies were performed. Radiographic studies are not required to satisfy these response requirements. Bone marrow, plasmacytoma, and skeletal survey assessments are not required to be confirmed by repeat testing. SD requires a duration of  $\geq 6$  weeks.
- c Presence/absence of clonal cells is based upon the  $\kappa/\lambda$  ratio. An abnormal  $\kappa/\lambda$  ratio by immunohistochemistry and/or immunofluorescence requires a minimum of 100 plasma cells for analysis. An abnormal ratio reflecting presence of an abnormal clone is  $\kappa/\lambda$  of  $> 4:1$  or  $< 1:2$ .
- d **Determination of PD while on study requires 2 consecutive assessments** made at any time before classification of PD and/or the institution of new therapy. Serum M-component increases of  $\geq 1$  g/dL from nadir are sufficient to define progression if nadir M-component is  $\geq 5$  g/dL.
- e Plasmacytomas: A definite increase in the size is defined as a  $\geq 50\%$  increase as measured serially by the sum of the products of the cross-diameters of the measurable lesion. A plasmacytoma is considered measurable if the longest diameter is at least 1 cm and the product of the cross diameters is at least 1 cm^2. Plasmacytomas of lesser size will be considered non-measurable.
- f The requirement for bi-directional measurements applies only to plasmacytomas.
- g The plasmacytoma specifications for PD are based on interpretation of the IMWG-URC and practical considerations for study execution.

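### The calcium limit for myeloma progression is given as 11.5 mg/dL or 2.65 mmol/L, which are two different limits; Appendices E and G need one reconciled value.

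*Protocol*

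**What the plan says.** Protocol Appendix E, the myeloma response criteria used on study, lists new hypercalcemia among the grounds for progressive disease, with a corrected serum calcium above "11.5 mg/dL or 2.65 mmol/L) that can be attributed solely to the plasma cell proliferative disorder". Appendix G, which inclusion criterion 103 cites for relapsed or refractory disease, repeats the same pair of figures: above 11.5 mg/dL or 2.65 "mmol/l) that can be attributed solely to the plasma cell proliferative disorder".

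In both places one ground is enough; Appendix G's wording is that progression "requires any one or more of the following". For subjects on study, Appendix E adds a confirmation rule: "Determination of PD while on study requires 2 consecutive assessments". Bone marrow, plasmacytoma and skeletal survey findings are exempt from repeat testing. Calcium is not.

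Protocol Section 6.2.1.3 makes progression a reason to stop treatment permanently: "Disease progression according to IMWG (MM), Lugano classification (NHL), or 2017 ELN response criteria (AML", with institutional guidelines as a further or alternative basis. SAP Section 5 uses progression as an event in PFS and duration of response, names IMWG-URC as the myeloma criteria by investigator assessment, and states no calcium limit of its own.

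Elsewhere the protocol does give a usable calcium conversion. The hypocalcemia row of Section 6.5.7 has "7.0 mg/dL (1.75 mmol/L"), and Appendix L has the same pair.

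**The concern.** A limit printed in two units should be the same limit twice. Here it is not, and the difference is too large to be rounding. A subject whose corrected calcium lies between the two figures has progressed by one and not by the other, and the text does not say which governs.

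What is at stake is a progression call. Through Appendix E, that call sets the event date for PFS and duration of response and is a ground for discontinuation. Protocol Section 3.2 places sites in Australia, Europe, Japan and the United States, and Section 7.4.2 allows local as well as central laboratories, so use of both unit systems is plausible. The groups are small, so a single reclassified subject would be visible: 10 percentage points in a myeloma expansion group of 10 (Protocol Section 10.3), or 5 points in an expansion group of 20 (Part 3C, SAP Section 3.2).

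**Working it through.** **Inputs**

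- Stated pair for progression: 11.5 mg/dL and 2.65 mmol/L (Protocol Appendices E and G).
- Stated pair for low calcium: 7.0 mg/dL and 1.75 mmol/L (Protocol Section 6.5.7 and Appendix L).
- Molar mass of calcium, 40.078 g/mol, a physical constant used only as a cross-check.

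**Step 1. The protocol's own factor.** 1.75 / 7.0 = 0.25 mmol/L per mg/dL. By molar mass, 7.0 mg/dL is 70 / 40.078 = 1.747 mmol/L, which rounds to the stated 1.75. The low-calcium pair is sound.

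**Step 2. Try to reproduce 2.65 from 11.5.**

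- Protocol factor: 11.5 × 0.25 = 2.875 mmol/L.
- Molar mass: 115 / 40.078 = 2.869 mmol/L.

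Neither gives 2.65.

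**Step 3. Convert the other way.**

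- Protocol factor: 2.65 / 0.25 = 10.6 mg/dL.
- Molar mass: 2.65 × 40.078 / 10 = 10.62 mg/dL.

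**Step 4. Size of the gap.**

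- In mmol/L: 2.869 − 2.65 = 0.22.
- In mg/dL: 11.5 − 10.6 = 0.9 (0.88 by molar mass).
- Relative to 11.5 mg/dL: 0.9 / 11.5 = 7.8% (7.6% by molar mass).

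**Step 5. What the gap does to a classification** (molar-mass conversion):

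| Corrected calcium, mg/dL | mmol/L | Above 11.5 mg/dL? | Above 2.65 mmol/L? |
|---|---|---|---|
| 10.5 | 2.62 | no | no |
| 10.7 | 2.67 | no | yes |
| 11.0 | 2.74 | no | yes |
| 11.4 | 2.84 | no | yes |
| 11.6 | 2.89 | yes | yes |

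The figures disagree only between about 10.6 and 11.5 mg/dL.

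**Step 6. Is dual-unit conversion loose elsewhere?** No, in the pairs checked. Uric acid 8 mg/dL is 80 / 168.11 × 1000 = 476 µmol/L, as printed. Phosphorus 4.5 mg/dL is 45 / 30.974 = 1.45 mmol/L, as printed. Phosphorus 5.0 mg/dL is 50 / 30.974 = 1.614 mmol/L, against a printed 1.615. Among the pairs checked, only this one fails.

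**The case against.** The arithmetic is not in dispute. The case on the other side is about consequence, and much of it stands.

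- **Mixed units are not documented.** A reader might infer that progression in this trial does depend on the unit each laboratory reports. The documents do not support that as fact: nowhere do they state a laboratory's reporting unit. It remains an assumption, plausible from the countries and the local laboratories.
- **The word *or* can be read literally.** If exceeding either figure suffices, every site has one effective limit, the lower. That removes the inconsistency between sites but leaves the 11.5 mg/dL figure doing nothing, since any value above it already exceeds 2.65 mmol/L. The documents do not say this reading is meant, and a site working in mg/dL would naturally apply 11.5.
- **Eligibility.** A reader might infer that entry as relapsed or refractory varies with the unit. That is remote. Inclusion criterion 104 separately requires measurable disease by M-protein or free light chain, and Appendix G also accepts non-response on therapy as refractory. Only a subject whose sole qualifying evidence was a calcium in the narrow band would be affected.
- **Discontinuation.** The calcium limit is not the only route: institutional guidelines and clinically significant deterioration are also listed in Section 6.2.1.3.
- **Analysis.** The protocol restricts PFS to dose expansion (Section 10.6.3.1). The SAP tests no hypothesis (Section 2.2) and may omit time-to-event summaries with fewer than 10 events (Section 9.5).
- **Confirmation.** Two consecutive assessments reduce chance misclassification. They do not help if the same figure is applied both times.
- **Source.** Appendix E is adapted from published criteria and marked as modified for the protocol. Whether the pair was inherited cannot be checked here, and origin would not make the figures equal.

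**Conclusion.** The point holds as an internal inconsistency in a decision threshold: the two figures in Appendices E and G differ by about 0.22 mmol/L, or 0.9 mg/dL (about 8%), by the protocol's own conversion.

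The practical effect is probably small, and the documents give no frequency from which to estimate it. It needs a corrected calcium of about 10.6 to 11.5 mg/dL, newly developed and attributed solely to myeloma, with no other progression criterion met and, on study, confirmation at two consecutive assessments. A difference between sites needs the further assumption that they report in different units. Where all of this occurs, PFS, duration of response and discontinuation for progression are affected through Appendix E; eligibility, through Appendix G, only remotely.

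One limit on scope: SAP Section 1 refers to protocol amendment 4, while the protocol reviewed carries amendment 1. Myeloma remains in SAP Parts 2C and 3C, but whether the later protocol keeps this pair cannot be seen.

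**What to change.** State one calcium limit for myeloma progression in Appendices E and G, correctly converted in both units. The sponsor must say which of the two values is intended; the documents do not settle it and no choice is made here. Check whether the pair persists in the amendment to which the SAP refers, and correct it there too if so.

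The cost is wording in two appendices. No design element, sample size or analysis method changes.

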**Relapse after complete remission for patients with AML is defined as:**

- Bone marrow blasts  $\geq 5\%$ ; or
- reappearance of blasts in the blood; or
- development of extramedullary disease

These response criteria were published in 2010, "Diagnosis and management of acute myeloid leukemia in adults: Recommendations from an international expert panel, on behalf of the European Leukemia Net" ([Döhner et al, 2010](#)).

The criteria for progressive disease were suggested in the 2017 ELN recommendations ([Döhner et al, 2017](#)).

Approved

## Appendix H. World Health Organization Classification for Acute Myeloid Leukemia

Definition AML:  $\geq 20\%$  myeloblasts in blood or in bone marrow

Abnormal promyelocytes in acute promyelocytic leukemia, promonocytes in AML with monocytic differentiation and megakaryoblasts in acute megakaryocytic leukemia are considered blast equivalents. **Patients with APML are not eligible for this study.**

First, AML should be classified as AML with recurrent cytogenetic abnormalities. If this is not applicable the leukemia is classified as AML with multilineage dysplasia or therapy related and if this subtype is also not applicable as AML not otherwise categorized.

Acute Myeloid Leukemia and Related Precursor Neoplasms, and Acute Leukemias of Ambiguous Lineage ([Arber et.al, 2016](#)).

### AML and related neoplasms

AML with recurrent genetic abnormalities AML with t(8;21)(q22;q22.1); *RUNX1-RUNX1T1*

AML with inv(16)(p13.1q22) or t(16;16)(p13.1;q22);  
*CBFB-MYH11*

Acute promyelocytic leukemia with *PML-RARA\**

AML with t(9;11)(p21.3;q23.3); *MLLT3-KMT2A†*

AML with t(6;9)(p23;q34.1); *DEK-NUP214*

AML with inv(3)(q21.3q26.2) or t(3;3)(q21.3;q26.2);  
*GATA2,MECOM(EVI1)*

AML (megakaryoblastic) with t(1;22)(p13.3;q13.3);  
*RBM15-MKL1‡*

Provisional entity: AML with *BCR-ABL1*

AML with mutated *NPM1§*

AML with biallelic mutations of *CEBPA§*

Provisional entity: AML with mutated *RUNX1*

AML with myelodysplasia-related changes||

Therapy-related myeloid neoplasms{

AML, NOS

AML with minimal differentiation

AML without maturation

AML with maturation

Acute myelomonocytic leukemia

Acute monoblastic/monocytic leukemia #

Acute megakaryoblastic leukemia

Acute basophilic leukemia

Acute panmyelosis with myelofibrosis

Footnotes defined on next page

Approved

Myeloid sarcoma	
Myeloid proliferations related to Down syndrome	Transient abnormal myelopoiesis Myeloid leukemia associated with Down syndrome
Blastic plasmacytoid dendritic cell neoplasm	
Acute leukemias of ambiguous lineage	Acute undifferentiated leukemia MPAL with t(9;22)(q34.1;q11.2); BCR-ABL1 ** MPAL with t(v;11q23.3); KMT2A rearranged MPAL, B/myeloid, NOS MPAL, T/myeloid, NOS

For a diagnosis of AML, a marrow blast count of  $\geq 20\%$  is required, except for AML with the recurrent genetic abnormalities t(15;17), t(8;21), inv(16), or t(16;16). Adapted from Arber et al. MPAL, mixed phenotype acute leukemia; NK, natural killer.

\* Other recurring translocations involving *RARA* should be reported accordingly: for example, AML with t(11;17)(q23;q12); *ZBTB16-RARA*; AML with t(11;17)(q13;q12); *NUMA1-RARA*; AML with t(5;17)(q35;q12); *NPM1-RARA*; or AML with *STAT5B-RARA* (the latter having a normal chromosome 17 on conventional cytogenetic analysis).

† Other translocations involving *KMT2A* (*MLL*) should be reported accordingly: for example, AML with t(6;11)(q27;q23.3); *MLLT4-KMT2A*; AML with t(11;19)(q23.3;p13.3); *KMT2A-MLLT1*; AML with t(11;19)(q23.3;p13.1); *KMT2A-ELL*; AML with t(10;11)(p12;q23.3); *MLLT10-KMT2A*.

‡ Rare leukemia most commonly occurring in infants.

§ Diagnosis is made irrespective of the presence or absence of multilineage dysplasia.

|| At least 20% ( $\geq 20\%$ ) blood or marrow blasts AND any of the following: previous history of MDS or MDS/MPN; myelodysplasia-related cytogenetic abnormality (see list below); multilineage dysplasia; AND absence of both prior cytotoxic therapy for unrelated disease and aforementioned recurring genetic abnormalities. Cytogenetic

abnormalities sufficient to diagnose AML with myelodysplasia-related changes are: Complex karyotype (defined as 3 or more chromosomal abnormalities in the absence of 1 of the WHO-designated recurring translocations or inversions, that is, t(8;21), inv(16) or t(16;16), t(9;11), t(v;11)(v;q23.3), t(6;9), inv(3) or t(3;3); AML with *BCRABL1*); Unbalanced abnormalities: 27 or del(7q); 25 or del(5q); i(17q) or t(17p); 213 or del(13q); del(11q); del(12p) or t(12p); idic(X)(q13); Balanced abnormalities: t(11;16)(q23.3;p13.3); t(3;21)(q26.2;q22.1); t(1;3)(p36.3;q21.2); t(2;11)(p21;q23.3); t(5;12)(q32;p13.2); t(5;7)(q32;q11.2); t(5;17)(q32;p13.2); t(5;10)(q32;q21.2); t(3;5)(q25.3;q35.1).

{ Cases should be classified with the related genetic abnormality given in the diagnosis.

# The former subgroup of acute erythroid leukemia, erythroid/myeloid type ( $\geq 50\%$  bone marrow erythroid precursors and  $\geq 20\%$  myeloblasts among nonerythroid cells) was removed; myeloblasts are now always counted as percentage of total marrow cells. The remaining subcategory AML, NOS, pure erythroid leukemia requires the presence of  $>80\%$  immature erythroid precursors with  $\geq 30\%$  proerythroblasts.

\*\* *BCR-ABL1* leukemia may present as MPAL; treatment should include a tyrosine kinase inhibitor.

Approved

